2.5 DEFINITION OF 48-WEEK DATA

All screening and post-baseline data with a clinical date (i.e., administration/assessment/onset/start date) on or before the defined Week 48 data cutoff date will be included in the primary 48-week analysis. The 48-week data cutoff will include all data regardless of the type of study visit at which it was collected. This may

include data collected at unscheduled visits or early termination visits, if the visit date was on or before the 48-week data cutoff date. The data cutoffs for Week 48 data are defined as follows:

- **For all assessments except imaging and microperimetry:** The Week 48 data cutoff will be Study Day 350 (i.e., Study Day 337 [Week 48 day]+ 13 day window) for the Q4W treatment arms and Study Day 357 (i.e., Study Day 337 [Week 48 day]+20 day window) for the Q6W treatment arms.
- **For all imaging (including FAF) and microperimetry assessments:** The Week 48 data cutoff will be Study Day 384 (i.e., Study Day 337 [Week 48 day]+47 day window) for all treatment arms. The wider analysis window for imaging and microperimetry assessments is to allow for capture of missed images that were taken at the next scheduled visit, as permitted by the protocol.

3. STUDY CONDUCT

3.1 RANDOMIZATION

Patients are randomized to the treatment arms through an IxRS. After all patient eligibility requirements are confirmed at both the screening and Day 1 visit, patients are randomized in a 2:1:2:1 ratio to one of four arms (10 mg lampalizumab Q4W, sham Q4W, 10 mg lampalizumab Q6W, or sham Q6W). Study treatment is to be initiated on the same day that the patient is randomized (Day 1 visit).

Randomization is stratified by biomarker status (positive vs. negative, as determined by the cobas[®] CFI Profile CTA), baseline BCVA ETDRS chart Snellen equivalent (20/50 or better vs. worse than 20/50), sex (male vs. female), and microperimetry eligibility (yes vs. no). A permuted-block randomization method is used to obtain an approximately 2:1 ratio between lampalizumab and sham arms for each dosing frequency within each stratum.

Once the study randomizes the allotted number of CFI profile biomarker-positive or CFI profile biomarker-negative patients necessary to achieve the targeted 1.5:1 ratio for biomarker groups (see Section 2.2), the additional screened patients who would have been randomized in the already filled biomarker group will be screen-failed.

Following randomization and during the treatment period, the IxRS makes study treatment kit assignments.

Patient randomization and study treatment kit assignments are verified on an ongoing basis by an external and independent data coordinating center (iDCC). The iDCC independently reviews the logs to ensure that randomization and kit assignments are conducted correctly by the IxRS.

3.2 INDEPENDENT DATA REVIEW

3.2.1 Central Reading Center

All ocular images and microperimetry results are obtained by trained site personnel at the study sites and forwarded to an external central reading center for independent analysis and storage. As part of the screening process, the central reading center evaluates ocular images and microperimetry results to provide an objective assessment of patient eligibility. Throughout the study, the central reading center evaluates ocular images and microperimetry data in an objective and masked manner (masked to patient treatment assignment), with resulting data forwarded to the Sponsor electronically.

3.2.2 Independent Data Monitoring Committee

An independent Data Monitoring Committee (iDMC) monitors safety and study conduct on an ongoing basis. Members of the iDMC are external to the Sponsor and follow a charter that outlines the iDMC roles and responsibilities. The iDMC meets approximately every 6 months (frequency adjustable as required) to review unmasked safety and study conduct data prepared by an external iDCC. Further, the iDMC may review efficacy data if deemed necessary to assess the benefit-risk profile of lampalizumab.

The iDMC may recommend stopping the study early for safety reasons. No formal efficacy or futility analysis is planned for the study. While there are no formal efficacy or futility analyses, per FDA request, a nominal Type I error penalty of 0.0001 will be taken for each time the iDMC reviews unmasked data reports prior to the formal analysis of the primary efficacy endpoint. At the time of the primary efficacy endpoint analysis, four scheduled data reviews will have been conducted by the iDMC (July 2015, February 2016, August 2016, and March 2017); therefore, analyses of the primary efficacy endpoint will be performed at $\alpha = 0.0496$.

4. STATISTICAL METHODS

4.1 ANALYSIS POPULATIONS

Two main analysis populations are defined for this study: the intent-to-treat (ITT) population and the safety-evaluable population. In addition, as microperimetry assessments and serial ECG evaluations were each performed on a subset of patients at selected study sites, a microperimetry-analysis population and an ECG-analysis population are defined.

4.1.1 Intent-to-Treat Population

The ITT population will be comprised of all patients who were randomized in the study. For analyses based on this patient population, patients will be grouped according to the treatment assigned at randomization.

4.1.2 Safety-Evaluable Population

The safety-evaluable population will be comprised of all patients who received at least one injection of study treatment (lampalizumab or sham injection). For analyses based on this patient population, patients will be grouped according to the actual treatment received as follows. Patients who receive only sham injections will be classified in the sham treatment arm with the frequency (Q4W or Q6W) as assigned at randomization. Any patient who receives one or more injection of lampalizumab will be classified in the lampalizumab treatment arm with the frequency (Q4W or Q6W) as assigned at randomization. This includes patients randomized to sham who accidentally received one or more injections of lampalizumab.

It is expected that most patients will receive their assigned treatment at all dosing timepoints and that only a small number of dosing errors will occur. Nonetheless, dosing errors will be reviewed in conjunction with the corresponding patient safety data to assess for any impact on the defined safety populations or the overall safety conclusions.

4.1.3 Microperimetry-Analysis Population

Microperimetry assessments were performed on a subset of patients at selected study sites only. The microperimetry analysis population will be comprised of all ITT patients with microperimetry assessments who met the microperimetry eligibility criteria as evaluated by the central reading center, and validation checks will be applied to identify microperimetry assessments of sufficient quality for inclusion in the analysis. For analyses based on this patient population, patients will be grouped according to the treatment assigned at randomization. Due to the smaller sample size enrolled than anticipated, statistical inferences for efficacy endpoints based on microperimetry assessments will be based on pooled data from Studies GX29176 and GX29185.

4.1.4 ECG-Analysis Population

Electrocardiogram assessments were performed on a subset of patients at selected U.S. study sites only. The ECG-analysis population will be comprised of all safety-evaluable patients who did not have atrial fibrillation at baseline per ECG assessment, and who had numerical results reported from at least one ECG assessment. For analyses based on this patient population, patients will be grouped according to the actual treatment received, consistent with patient groupings for the safety-evaluable population.

4.2 DEFINITION OF BASELINE

Baseline will be defined as the last available pre-treatment value taken on or before the day of randomization, and will be used for summary of demographic characteristics, as well as for all change-from-baseline analyses of efficacy and safety endpoints.

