Note: if the study eye is treated with a Lucentis injection during the same visit as the study treatment (lampalizumab/sham), the treatment with Lucentis has to be performed first. Please measure and record the post-Lucentis treatment IOP value on the appropriate eCRF.

The method of IOP measurement used for a patient must remain consistent throughout the study.

Ocular Imaging and Microperimetry

The central reading center will provide sites with the Central Reading Center manual and training materials for specified study ocular images and microperimetry (at selected sites). Before any study images and microperimetry are obtained, site personnel, test images, and systems and software (where applicable) will be certified/validated by the reading center as specified in the Central Reading Center manual. All ocular images and microperimetry results will be obtained by trained site personnel at the study sites and forwarded to the central reading center for independent analysis and/or storage (see [Appendix 10](#), [Appendix 11](#), [Appendix 12](#), [Appendix 13](#), [Appendix 14](#), and [Appendix 15](#)).

Note: after randomization, if a patient misses a study visit during which ocular images were scheduled to be taken (see [Appendix 1](#)), the images should be obtained at the next scheduled visit.

Ocular images, keratometry, and microperimetry obtained include the following:

- Stereoscopic, CFP of both eyes
- FAs of both eyes (performed after laboratory samples are obtained)
- FAF (with keratometry measurements), near infrared (NI), and spectral domain optical coherence tomography (SD-OCT) images of both eyes
- Mesopic Microperimetry (at selected sites) of selected study eye only; to account for testing learning curve, patient is allowed up to 3 attempts to meet screening criteria

Note: if the Investigator determines that both eyes of a patient meet the eligibility criteria for study eye, mesopic microperimetry will be performed on both eyes at screening.

Additional details on obtaining these images, keratometry, and microperimetry are included in the Central Reading Center Manual.

Lampalizumab—F. Hoffmann-La Roche Ltd
64/Protocol GX29176, Version 6

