Appendix 1 Schedule of Assessments (cont.)

Table 1 Study Flowchart for Q4W Arms: Day 1, Day 8, Week 4 through Week 52, and Early Termination (cont.)

	Screening	Day		Week Visit													Early Term ^a	
		1	8	4	8	12	16	20	24	28	32	36	40	44	48	52		
Assessment Windows (Days)	-28 to -1	NA	±2	±5	±5	±5	±5	±5	±5	±5	±5	±5	±5	±5	±5	±5	±5	See footnote a
CFI whole blood sample (SF patients included) ^{f, h}	x																	
CFI buccal swab sample (SF patients included) ^{f, h}	x																	
Biomarker plasma sample ^f		x																
Biomarker paxgene sample ^f		x																
Biomarker whole blood clinical genotyping sample ^f		x																
Serum pregnancy sample ^{f, i, j}	x																	x
Urine pregnancy test ^{f, j}		x		x	x	x	x	x	x	x	x	x	x	x	x	x	x	
Serum ATA sample ^f		x							x							x		x
Serum PK sample for lampalizumab concentration ^f		x	x	x					x							x		x
Optional aqueous sample ^f		x							x					x				
AH50 sample ^f		x														x		x
BCVA testing (starting at 4 m) ^k	x	x	x	x	x	x	x	x	x	x	x	x	x	x	x	x	x	x
LL BCVA testing (starting at 4 m) ^k		x							x							x		x
MNRead or Radner Reading Charts ^{k, l}		x														x		x

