Appendix 1 Schedule of Assessments (cont.)

Table 1 Study Flowchart for Q4W Arms: Day 1, Day 8, Week 4 through Week 52, and Early Termination (cont.)

	Screening	Day		Week Visit													Early Term ^a	
		1	8	4	8	12	16	20	24	28	32	36	40	44	48	52		
Assessment Windows (Days)	-28 to -1	NA	±2	±5	±5	±5	±5	±5	±5	±5	±5	±5	±5	±5	±5	±5	±5	See footnote a
Pre-treatment IOP measurement ^k	x	x	x	x	x	x	x	x	x	x	x	x	x	x	x	x	x	x
Mesopic microperimetry at selected sites (study eye only) ^m	x	x							x							x		x
Slit-lamp examination	x	x	x	x	x	x	x	x	x	x	x	x	x	x	x	x	x	x
Dilated binocular indirect ophthalmoscopy	x	x	x	x	x	x	x	x	x	x	x	x	x	x	x	x	x	x
FAF ⁿ	x								x			x				x		x
Keratometry ⁿ	x																	
SD-OCT ⁿ	x								x							x		x
Near infrared imaging ⁿ	x								x			x				x		x
Fundus photography ⁿ	x															x		x
Fluorescein angiography ⁿ	x															x		x
Administration of lampalizumab injection/sham to study eye		x		x	x	x	x	x	x	x	x	x	x	x	x	x	x	
Post-treatment finger counting and IOP measurement ^o		x		x	x	x	x	x	x	x	x	x	x	x	x	x	x	
Concomitant medications ^p	x	x	x	x	x	x	x	x	x	x	x	x	x	x	x	x	x	x
Adverse events ^q	x	x	x	x	x	x	x	x	x	x	x	x	x	x	x	x	x	x
Concurrent ocular procedures ^r		x	x	x	x	x	x	x	x	x	x	x	x	x	x	x	x	x
Follow-up call ^s				x	x	x	x	x	x	x	x	x	x	x	x	x	x	

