4.5.2 Secondary Efficacy Endpoints

The secondary efficacy endpoints are listed in Section 2.1.2. At the time of primary analysis, all secondary endpoints will be evaluated based on data from baseline to Week 48 (see Section 2.4). At the time of the final study analysis, all secondary endpoints will be evaluated based on data from baseline to Week 96.

Analysis of secondary efficacy endpoints assessed by mesopic microperimetry will be based on the microperimetry-analysis population. Statistical inferences for efficacy endpoints based on microperimetry assessments will be based on pooled data from Studies GX29176 and GX29185. Analysis of all other secondary efficacy endpoints will be based on the ITT patient population.

Hypothesis testing for three key secondary endpoints will be performed in the order specified in Section 4.5.2.1 based on the Week 96 timepoint. Subgroup analyses (Section 4.5.2.2) for the key secondary efficacy endpoints will be performed.

Treatment-effect related analyses to compare each lampalizumab treatment arm (Q4W or Q6W) and the pooled sham arm for secondary efficacy endpoints will be undertaken as follows. In general, continuous secondary endpoints will be analyzed using a MMRM analysis, with change from baseline as the response variable. For the Week 48 analyses, post-baseline visits, up to and including Week 48, will be included. For the Week 96 analyses, post-baseline visits, up to and including Week 96, will be included. Independent variables for treatment arm, study visit (categorical variable), treatment arm by study visit interaction, baseline value of the endpoint, and the randomization stratification factors and baseline covariates as described in Section 4.5 will be included in the model. An unstructured covariance matrix will be used to model the within-subject errors. If there are convergence problems with the model, then a heterogeneous compound symmetry covariance structure will be used.

In general, binary secondary endpoints will be analyzed using a logistic regression model. The model will include independent variables for treatment arm, baseline value of the endpoint (continuous scale), and the randomization stratification factors and baseline covariates as described in Section 4.5, as appropriate. If the response rate is low, an unadjusted analysis may be performed. Analyses will be based on the observed data for the timepoint, with no imputation for missing data.

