For analyses of BCVA, the model will include the major assessment timepoints of Weeks 12, 24, 36, 48, 60, 72, 84, and 96 that are in common between the Q4W and Q6W dosing arms. In addition, the stratification factor of baseline BCVA category will not be included in the model, given baseline BCVA is included as a continuous covariate.

Reading speed will be calculated per the MNRead or Radner user's manuals, with no adjustment for reading inaccuracy. An addition step to cap resulting reading speed values at a maximum of 300 words per minute will be implemented. Values above 300 words per minute exceed values reported in the literature for adults with no vision impairment for MNRead (Calabrese et al. 2016) or Radner (Radner et al. 2002; Radner and Diendorfer 2014) assessments. Maximum reading speed will be calculated as the mean of the three highest reading speeds obtained per the user's manuals. Data collected via the two reading charts will be pooled for analysis and the model will include an additional covariate for reading chart type (MNRead or Radner). Additional subgroup analyses will be performed to assess the consistency of finding across the two reading charts (see Section 4.5.2.2).

NEI VFQ-25 scores (composite, near activity subscale, and distance activity subscale) and mean FRI Index scores will be calculated per the scoring algorithms in the corresponding user's manuals.

For analyses of binocular maximum reading speed, NEI VFQ-25 composite score, NEI VFQ-25 near activity subscale score, NEI VFQ-25 distance activity subscale score, and mean FRI Index score, an additional adjustment for baseline BCVA of the better seeing eye will be included (instead of study eye baseline BCVA [20/50 or better vs. worse than 20/50]). In the event that baseline BCVA is missing for the study or fellow eye (but not both), then the non-missing baseline BCVA will be used for this covariate.

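### The microperimetry models leave the screening reading unused; adding it as a second baseline covariate is a free but modest gain in precision for H05

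*SAP*

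**What the plan says.** SAP 4.2 sets one rule for every change-from-baseline analysis: "Baseline will be defined as the last available pre-treatment value taken on or before the day of randomization". SAP 4.5.2 then specifies the MMRM for continuous secondary endpoints: "Independent variables for treatment arm, study visit (categorical variable), treatment arm by study visit interaction, baseline value of the endpoint", plus the stratification factors and covariates of SAP 4.5. That is one baseline value per endpoint.

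In both flowcharts of Protocol Appendix 1 (Q4W and Q6W), the row that begins "Mesopic microperimetry at selected sites (study eye only" is marked at Screening and on Day 1, before the first injection. Protocol 4.5.5 adds that, at screening, "to account for testing learning curve, patient is allowed up to 3 attempts to meet screening criteria".

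SAP 4.1.3 moves microperimetry inference to data pooled from GX29176 and GX29185. Its reason is: "Due to the smaller sample size enrolled than anticipated". SAP 4.5.2.1 puts the microperimetry population at 10-15% of ITT. It tests H06 confirmatorily only if pooled H05 is rejected, and H07 only if H06 is rejected.

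For contrast, BCVA is also marked at Screening and Day 1, and its model has one continuous baseline value. The row that begins "LL BCVA testing (starting at 4 m" is marked before treatment on Day 1 only, and so are the reading charts.

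**The concern.** Microperimetry depends on patient effort, so a single reading is an imperfect measure of the patient's pre-treatment state. Error in the one baseline covariate stays in the residual variance of the adjusted comparison. A second pre-treatment reading is scheduled for these patients, but no SAP model uses it when the Day 1 value is available, and the SAP does not say why.

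H05 is where this matters most. Its population is small enough that two trials are pooled, and failing H05 closes confirmatory testing of LLVA and reading speed for that dose and population.

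**Working it through.** **Inputs from the documents.** Protocol 6.1: difference 6.91 points, SD of change 9.88, two-sided α 0.05, 25% dropout, 46 biomarker-positive patients per lampalizumab group and 23 per sham group (46 pooled), 80% power. Protocol 3.1.1: about 138 + 90 = 228 microperimetry patients planned, which is 24% of 936. SAP 4.5.2.1: 10-15% of ITT expected, α 0.0496.

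**The plan's own figure.** For a two-sample t-test (noncentral t), 33 completers per group give 79.9% power and 34 give 81.1%. Then 34/0.75 = 45.3, so 46 per group. The stated sizing reproduces.

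**Size available for H05.** 10-15% of 936 is 94-140 patients. Assuming GX29185 is of the same size, the pool is 187-281 patients, or 62-94 per analysis group (three equal groups once sham is pooled). After 25% dropout this leaves about 47-70 completers per group.

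**Variance model.** The documents give neither the test-retest SD (e) nor the SD between patients in the true baseline (B), so both are assumed. With V = 9.88² − 2e² (true change):

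- one reading: V + e² + 1/(1/B² + 1/e²)
- two readings, screening SD = k·e: V + e² + 1/(1/B² + 1/e² + 1/(k²e²))

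Example with e = 3, B = 12, k = 1:

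- V = 97.61 − 18 = 79.61
- one reading: 79.61 + 9 + 8.47 = 97.08
- two readings: 79.61 + 9 + 4.36 = 92.98 (rounded from unrounded terms)
- reduction: 4.10/97.08 = 4.2%

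Reduction in residual variance:

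| e (points) | k=1, B=12 | k=1.5, B=12 | k=2, B=12 | k=1, B=6 |
|---|---|---|---|---|
| 2 | 2.0% | 1.2% | 0.8% | 1.8% |
| 3 | 4.2% | 2.6% | 1.7% | 3.3% |
| 4 | 7.1% | 4.3% | 2.8% | 4.9% |
| 5 | 10.4% | 6.2% | 4.0% | 6.3% |

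With k = 1, B from 10 to 14 gives 1.9-2.0%, 4.1-4.3%, 6.7-7.4% and 9.6-11%. The B = 6 column stands for other covariates already explaining much of the between-patient variance.

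**Cross-check with correlations.** Let r be the Screening to Day 1 correlation and ρ the baseline to Week 96 correlation. For equally good readings the variance ratio is [1 − 2ρ²/(1+r)]/(1 − ρ²). For r = 0.8 and ρ = 0.6 this is 0.60/0.64 = 0.94; for r = 0.9 and ρ = 0.7 it is 0.95; for r = 0.95 and ρ = 0.6 it is 0.99. Most of the grid examined (r 0.7-0.95, ρ 0.4-0.8) is worth 1-12% more patients. The corner ρ = r = 0.7-0.8 reaches 20-25%, but there the whole SD of change would be measurement error. If the screening reading correlates with Week 96 at only 0.9ρ, the ratio is 0.93-1.00, with no gain at r = 0.9.

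**Power for H05, two-sided α 0.0496, equally good readings.** Here the residual SD with one reading is 9.88·√[(1−ρ²)/(2(1−ρ))], assuming equal variances.

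| Completers per group | Difference | r, ρ | One reading | Two readings |
|---|---|---|---|---|
| 47, overall | 6.91 | 0.8, 0.6 | 96.3% | 97.2% |
| 47, overall | 6.91 | 0.8, 0.7 | 95.3% | 97.0% |
| 70, overall | 6.91 | 0.8, 0.7 | 99.4% | 99.7% |
| 47, overall | 5.0 (assumed) | 0.8, 0.7 | 74.8% | 79.5% |
| 28, biomarker-positive (60% assumed) | 6.91 | 0.8, 0.7 | 79.5% | 83.8% |

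The error-SD model with 47 completers, 6.91 points and B = 12 gives 91.8% to 92.3% at e = 2 and 92.7% to 95.1% at e = 5. The starting power is lower but the gain is similar.

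**The case against.** The strongest reply is that nothing is wrong here. The last pre-treatment value is a conventional baseline that causes no bias and leaves the type I error untouched. That stands in full: a reader might infer that the SAP's rule is an error or that it weakens the validity of H05, and the documents do not support either.

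Two further inferences also go too far. One is that the screening reading can never enter a model. SAP 4.2 takes the last available value, so a patient without a Day 1 value is analysed from screening. The other is that the two readings are independent replicates of equal quality. Protocol 4.5.5 acknowledges a learning curve and allows several attempts, and Protocol 4.1.3 selects the screening test on duration and false-positive rate. The equal-precision column above is therefore an upper case for each assumed e and B.

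The SAP has also already answered the small sample by pooling, and pooled power at the planned effect is above 90% in either model. BCVA does not strengthen the point: it is analysed in the full ITT population and is not one of the three key secondary endpoints.

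These objections limit the size of the gain but do not remove it. Learning does not bias the randomized comparison when the screening value enters as a separate covariate, and a further pre-treatment covariate does not raise the large-sample residual variance. Its cost is one degree of freedom.

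**Conclusion.** The point holds as an optional efficiency improvement, mainly for microperimetry. Residual variance falls by about 2-10% if the readings are equally precise. It falls by about 1-6%, or less, if the screening reading is noisier or the model's other covariates already explain part of the between-patient variance. It may not fall at all if the screening reading adds nothing beyond Day 1.

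At 6.91 points in the pooled overall population, power rises by about 1-2 points at the low end of the expected sample and by less than one point at the high end. Gains of about 2-5 points appear only where power is lower: a smaller assumed effect, or the biomarker-positive group alone.

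All of this rests on assumed test-retest and between-patient figures, on GX29185 being of similar size, and on GX29185 also having a screening reading, which these documents cannot confirm. H06 and H07 could benefit only through a better chance of passing H05, because LLVA and reading speed have no second pre-treatment reading.

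**What to change.** In SAP 4.5.2, before the Week 48 unmasking described in SAP 2.4, state the following for the pooled microperimetry MMRMs (absolute scotomatous points and mean macular sensitivity):

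- The study-eye screening value enters as a separate second baseline covariate and is not averaged with Day 1. Naming the eye matters because both eyes may be tested at screening.
- The value comes from the last screening attempt that met the Protocol 4.1.3 criteria and passed the SAP 4.1.3 validation checks.
- If that value is missing, the Day 1 value is used in its place.
- Change from baseline is still taken from Day 1, under the existing SAP 4.2 rule.
- The covariate applies provided GX29185 has the same screening reading, to be confirmed before the text is finalised.

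The same covariate in the BCVA model is optional. The cost is a few lines of SAP text and one degree of freedom, with no new visits, data or endpoint definitions. The timing matters because a covariate added after the Week 48 results have been seen would look data-driven.
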